1.1 Study design

Study CBYL719C2202 is a Phase II, multicenter, randomized, open-label, active-controlled trial designed to evaluate the safety and efficacy of the combination of dapagliflozin plus metformin XR compared to metformin XR alone during treatment with alpelisib plus fulvestrant, in participants with HR-positive, HER2-negative advanced breast cancer with a PIK3CA mutation following progression on or after endocrine-based therapy. The study will only include participants who have at least one of the following baseline risk factors for the development of severe hyperglycemia:

- Diabetes (fasting plasma glucose (FPG) ≥ 126 mg/dL or ≥ 7.0 mmol/L and/or HbA1c $\geq 6.5\%$)
- Pre-diabetes (FPG ≥ 100 mg/dL to < 126 mg/dL or 5.6 to < 7.0 mmol/L and/or HbA1c 5.7 to $< 6.5\%$)
- Obesity (BMI ≥ 30)
- Age ≥ 75 years

Approximately 132 participants was planned to be randomly assigned to one of the following treatment arms in a 1:1 ratio to receive either:

- Arm A: Alpelisib + fulvestrant + dapagliflozin + metformin XR
- Arm B: Alpelisib + fulvestrant + metformin XR

Randomization to treatment will be stratified by diabetic status at baseline, i.e., normal vs pre-diabetic/diabetic (based on FPG and/or HbA1c laboratory values).

The primary analysis will not be performed due to the permanent halt of recruitment and early termination of study. Only a final descriptive analysis will be conducted at the end of study (see Protocol Section 9.3).

No Data Monitoring Committee is planned for this study.

Figure 1-1 Study design

[figure not shown]
[figure not shown]

Figure 1-2 Study flow

1.2 Study objectives, endpoints and estimands

Objectives and related endpoints are described in [Table 1-1](#) below.

Table 1-1 Objectives and related endpoints

Objective(s)	Endpoint(s)
Primary objective(s)	Endpoint(s) for primary objective(s)

To evaluate the reduction in severe hyperglycemia events over the first eight weeks of alpelisib plus fulvestrant with prophylactic dapagliflozin plus metformin XR compared to alpelisib plus fulvestrant with prophylactic metformin XR	
Occurrence of severe hyperglycemia (grade ≥ 3, based on glucose laboratory values) over the first eight weeks of alpelisib plus fulvestrant treatment (from C1D8 to C3D8)
Secondary objective(s)	Endpoint(s) for secondary objective(s)

To evaluate alpelisib plus fulvestrant with prophylactic dapagliflozin plus metformin XR compared to alpelisib plus fulvestrant with prophylactic metformin XR with regard to preliminary efficacy parametersTo assess the safety and tolerability	
PFS, ORR with confirmed response and CBR with confirmed response, based on local radiology assessments and using RECIST 1.1 criteriaSafety: Incidence, type, and severity of adverse events per CTCAE version 4.03 criteria including changes in laboratory values, ECOG, vital signs, liver assessments, renal and cardiac assessments Tolerability: dose interruptions, reductions, dose intensity, and duration of exposure for all drug components

1.2.1 Primary estimand

The estimand is the precise description of the treatment effect and reflects strategies to address events occurring during trial conduct which could impact the interpretation of the trial results (e.g., premature discontinuation of treatment).

The primary scientific question of interest is: what is the effect on the occurrence of severe hyperglycemia (based on glucose laboratory values) over the first eight weeks of alpelisib plus fulvestrant (from Cycle 1 Day 8 to Cycle 3 Day 8) with prophylactic dapagliflozin plus metformin XR compared to alpelisib plus fulvestrant with prophylactic metformin XR, for participants with HR-positive, HER2-negative advanced breast cancer with a PIK3CA mutation, which progressed on or after endocrine-based therapy and have at least one risk factor for severe hyperglycemia, regardless of additional antihyperglycemic therapies as needed?

The justification for targeting this treatment effect is that we wish to assess the treatment effect based on the occurrence of severe hyperglycemia while the participants are exposed to alpelisib plus fulvestrant as well as after the discontinuation and interruption of prophylactic antihyperglycemic therapies, since any discontinuation or interruption will reflect clinical practice.

The primary estimand is characterized by the following attributes:

1. Population: participants with HR-positive, HER2-negative advanced breast cancer with a PIK3CA mutation, who progressed on or after endocrine-based therapy and have at least one risk factor for severe hyperglycemia; randomized and received at least one dose of study treatment.
Note: at least one dose of study treatment refers to at least one dose of any component of alpelisib, fulvestrant, dapagliflozin + metformin XR or metformin XR.
2. Treatment: the first study treatment is alpelisib plus fulvestrant with prophylactic dapagliflozin plus metformin XR (plus additional antihyperglycemic therapies as needed). The second study treatment is alpelisib plus fulvestrant with prophylactic metformin XR (plus additional antihyperglycemic therapies as needed).
3. Variable: occurrence of severe hyperglycemia (Grade ≥ 3 , based on glucose laboratory values) over the first eight weeks of alpelisib plus fulvestrant treatment (from Cycle 1 Day 8 to Cycle 3 Day 8). Further details are provided in [Section 2.5.1](#).
4. Handling of remaining intercurrent events:
 - Discontinuation of alpelisib for any reason or not receiving any alpelisib will be handled using treatment policy strategy.
 - Discontinuation and/or interruption of prophylactic antihyperglycemic therapies for any reason will be handled using treatment policy strategy.
 - Dose interruption and/or reduction of alpelisib for any reason will be handled using treatment policy strategy.

Details on how to handle intercurrent events are provided in [Section 2.5.3](#).

5. Summary measure: difference between treatment arms in percentage of participants with severe hyperglycemia.
Note: the primary analysis will not be performed due to the permanent halt of recruitment and early termination of study. Further details on the summary measure are provided in [Section 2.5.2](#).

2 Statistical methods

2.1 Data analysis general information

The analyses will be performed by Novartis. SAS version 9.4 or later will be used to perform all data analyses and to generate tables, figures, and listings.

Data included in the analysis

For the analysis, a cut-off date will be established after the follow-up has been documented. All statistical analyses will be performed using all data collected in the database up to the data

cut-off date. All data with an assessment date or event start date (e.g. vital sign assessment date or start date of an adverse event) prior to or on the cut-off date will be included in the analysis. Any data collected beyond the cut-off date will not be included in the analysis and will not be used for any derivations.

All events with start date before or on the cut-off date and end date after the cut-off date will be reported as ‘ongoing’. The same rule will be applied to events starting before or on the cut-off date and not having documented end date. This approach applies, in particular, to adverse event and concomitant medication reports. For these cases, the end date will not be imputed and therefore will not appear in the listings.

General analysis conventions

Pooling of centers: Unless specified otherwise, data from all study centers will be pooled for the analysis. Due to expected small number of participants enrolled at centers, no center effect will be assessed.

Qualitative data (e.g., gender, race, etc.) will be summarized by means of contingency tables by treatment group; a missing category will be included as applicable. Percentages will be calculated using the number of participants in the relevant population or subgroup as the denominator.

Quantitative data (e.g., age, body weight, etc.) will be summarized by appropriate descriptive statistics (i.e. mean, standard deviation, median, minimum, and maximum) by treatment group.

2.1.1 General definitions

2.1.1.1 Investigational drug and study treatment

Study treatment will refer to both alpelisib + fulvestrant + dapagliflozin + metformin XR and alpelisib + fulvestrant + metformin XR.

2.1.1.2 Date of first administration of study treatment component

The date of first administration is defined as the first date when a non-zero dose of that component of study treatment is administered and recorded on “Study Treatment” eCRF (for fulvestrant) or “Study Treatment Summary” eCRF (for alpelisib/dapagliflozin/metformin XR) for that component of study treatment.

2.1.1.3 Date of last administration of study treatment component

The date of last administration is defined as the last date when a non-zero dose of that component of study treatment is administered and recorded on the “Study Treatment” eCRF (for fulvestrant) or “Study Treatment Summary” eCRF (for alpelisib/dapagliflozin/metformin XR) for that component of study treatment.

2.1.1.4 Date of first administration of study treatment

The date of first administration of study treatment is defined as the first date when a non-zero dose of any component of study treatment (alpelisib or fulvestrant or dapagliflozin or metformin XR) is administered. The date of first administration of study treatment will also be referred to as the start of study treatment.

For example: if the first dose of alpelisib is administered on 08-Jan-2022, first dose of fulvestrant is administered on 01-Jan-2022, and first dose of dapagliflozin and metformin XR is taken on 03-Jan-2022, then the date of first administration of study treatment is 01-Jan-2022.

2.1.1.5 Date of last administration of study treatment

The date of last administration of study treatment is defined as the last date when a non-zero dose of any component of the study treatment (alpelisib or fulvestrant or dapagliflozin or metformin XR) is administered.

For example: if the last dose of alpelisib and fulvestrant is administered on 15-Apr-2022, and the last dose of dapagliflozin and metformin XR is taken on 17-Apr-2022, then the date of last administration of study treatment is on 17-Apr-2022.

2.1.1.6 Study day

The study day describes the day of the event or assessment date, relative to the reference start date.

The reference start date is designated as Study Day 1. Study Day -1 is the day that precedes Day 1. Study Day 0 is not defined. Study day is not to be used in numerical computations, for example in calculating exposure.

The study day will be calculated as follows:

- The date of the event (visit date, onset date of an event, assessment date etc.) - reference start date + 1 if the event is on or after the reference start date;
- The date of the event (visit date, onset date of an event, assessment date etc.) - reference start date if the event precedes the reference start date.

The reference start date for safety assessments (e.g. adverse event onset, laboratory abnormality occurrence, vital sign measurement, dose interruption etc.) is the start of study treatment.

The reference start date for all other, non-safety assessments (i.e., tumor assessment, disease progression, tumor response and ECOG performance status) is the date of randomization. (Example: if randomization date is 15-Dec-2021, start of study treatment is on 18-Dec-2021, and the date of death is 28-Dec-2021, then the study day when the death occurred is 14).

The study day will be displayed in data listings. If an event starts before the reference start date, the study day displayed on the listing will be negative.

2.1.1.7 Time Unit

A year length is defined as 365.25 days. A month length is 30.4375 days (365.25/12). If duration is reported in months, duration in days will be divided by 30.4375. If duration is reported in years, duration in days will be divided by 365.25.

2.1.1.8 Baseline

For efficacy evaluations, the last available assessment, including unscheduled assessments, on or before the date of randomization is taken as the “baseline” value or “baseline” assessment. In the context of baseline definition, the efficacy evaluations also include ECOG performance

status. For RECIST-based endpoints only, including PFS, ORR and CBR, a window of 7 days after the start of study treatment will be allowed, i.e. the investigator assessed responses will be considered as a candidate for the baseline assessment if the assessment is within 7 days after the treatment start date.

For safety evaluations (i.e. laboratory assessments, ECGs and vital signs), the last available assessment, including unscheduled assessments, on or before the start date of study treatment as described in [Section 2.1.1.4](#) is taken as “baseline” assessment. Assessments specified to be collected post-dose on the first date of treatment are not considered as baseline values.

If participants have no value as defined above, the baseline result will be considered missing.

2.1.1.9 On-treatment assessment/event

An on-treatment assessment event is defined as any assessment event in the following time interval:

- [date of first administration of study treatment; date of last administration of study treatment + 30 days], i.e. including the lower and upper limits

Note: the calculation of study treatment duration will use different rules as specified in [Section 2.4.2](#).

Safety summaries and selected summaries of deaths will summarize only on-treatment assessments/events.

An AE starting in the screening phase and ongoing in the on-treatment phase will not be considered an on-treatment AE unless it has worsened in severity.

If the last date of study treatment is missing, any assessment/event occurring after the start date of study treatment will be considered as on-treatment.

Data listings will include all assessments/events, flagging those which are not on-treatment assessments/events.

Note: The date of first administration of study treatment and the date of last administration of study treatment are defined in [Section 2.1.1.4](#) and [Section 2.1.1.5](#), respectively.

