2. Its relationship to the study treatment. If the event is due to lack of efficacy or progression of underlying illness (i.e. progression of the study indication) the assessment of causality will usually be 'Not suspected.' The rationale for this guidance is that the symptoms of a lack of efficacy or progression of underlying illness are not caused by the trial drug, they happen in spite of its administration and/or both lack of efficacy and progression of underlying disease can only be evaluated meaningfully by an analysis of cohorts, not on a single participant
3. Its duration (start and end dates or ongoing) and the outcome must be reported
4. Whether it constitutes a SAE (see [Section 10.1.2](#) for definition of SAE) and which seriousness criteria have been met
5. Action taken regarding with study treatment. All adverse events must be treated appropriately. Treatment may include one or more of the following:
  - Dose not changed
  - Dose reduced/increased
  - Drug interrupted/permanently discontinued
6. Its outcome

If the event worsens the event should be reported a second time in the eCRF noting the start date when the event worsens in toxicity. For Grade 3 and 4 adverse events only, if improvement to a lower grade is determined a new entry for this event should be reported in the eCRF noting the start date when the event improved from having been Grade 3 or Grade 4.

Conditions that were already present at the time of informed consent should be recorded in medical history of the participant.

Adverse events (including laboratory abnormalities that constitute AEs) should be described using a diagnosis whenever possible, rather than individual underlying signs and symptoms.

In general, adverse event monitoring should be continued for at least 30 days following the last dose of study treatment.

For participants who discontinue study treatment before Cycle 3, Day 8 hyperglycemia related adverse events should be collected up to 9 weeks after first dose of study treatment.

Once an adverse event is detected, it must be followed until its resolution or until it is judged to be permanent (e.g., continuing at the end of the study), and assessment must be made at each visit (or more frequently, if necessary) of any changes in severity, the suspected relationship to the interventions required to treat it, and the outcome.

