### **12.5.2 Safety endpoints**

For all safety analyses, the safety set will be used. All listings and tables will be presented by treatment group.

Safety summaries (tables, figures) include only data from the on-treatment period with the exception of baseline data which will also be summarized where appropriate (e.g., change from baseline summaries). In addition, a separate summary for death including on treatment and post treatment deaths will be provided. In particular, summary tables for adverse events (AEs) will summarize only on-treatment events, with a start date during the on-treatment period (treatment-emergent AEs).

The overall observation period will be divided into three mutually exclusive segments:

1. Pre-treatment period: from day of participant's informed consent to the day before first dose of study medication
2. On-treatment period: from day of first dose of study medication to 30 days after last dose of study medication
3. Post-treatment safety period: starting at day 31 after last dose of study medication.

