2.5.3 Handling of intercurrent events

The primary estimand will account for different intercurrent events as explained in the following:

- 1. Discontinuation of alpelisib or not receiving any alpelisib:** occurrence of severe hyperglycemia events collected after discontinuation of alpelisib or without any exposure to alpelisib will be used for the primary endpoint summary (treatment policy strategy)
- 2. Discontinuation and/or interruption of prophylactic antihyperglycemic therapies:** occurrence of severe hyperglycemia events collected after discontinuation and/or interruption of prophylactic antihyperglycemic therapies will be used for the primary endpoint summary (treatment policy strategy)

3. **Dose interruption and/or reduction of alpelisib:** occurrence of severe hyperglycemia events collected after dose interruption and/or reduction of alpelisib will be used for the primary endpoint summary (treatment policy strategy)

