2.7.1 Adverse events (AEs)

Summary tables for adverse events (AEs) will include only AEs that started or worsened during the on-treatment period, the treatment-emergent AEs. However, all safety data (including those from the pre and post-treatment periods) will be listed and those collected during the pre-treatment and post-treatment period are to be flagged. All information obtained on adverse events will be displayed by treatment group.

The number (and percentage) of participants with treatment emergent adverse events will be summarized by treatment, system organ class, preferred term and maximum severity. A participant with multiple grades for an AE will be summarized under the maximum grade recorded for the event. AEs with a missing CTCAE grade will be included in the 'All grades' column of the summary tables.

A participant with multiple adverse events within a system organ class is only counted once towards the total of the system organ class.

Separate summaries will be provided for serious adverse events if there are serious adverse events reported.

In AE summaries the system organ class will be presented alphabetically and the preferred terms will be sorted within SOC in descending frequency. The sort order for the preferred term will be based on their frequency in the dapagliflozin plus metformin XR treatment group.

The frequency of grade 3 and above AEs will be summarized separately.

All AEs, deaths, and serious adverse events (including those from the pre and post-treatment periods) will be listed by treatment group and those collected during the pre-treatment and post-treatment period will be flagged.

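### Adverse-event tables close 30 days after the last dose of any component, so some hyperglycemia AEs deliberately collected to study Day 64 reach only the listings

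*SAP*

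**What the plan says.** **Collection.** Protocol 6.1.5, 8.4.1 and 9.1.1 keep monitoring fasting plasma glucose in participants who stop both alpelisib and fulvestrant before Cycle 3 Day 8. Sections 6.1.5 and 9.1.1 give worked examples that also cover hyperglycemia-related AEs: stopping after 1 week means 8 more weeks, and after 2 weeks 7 more. Protocol 10.1.1 sets the limit: "hyperglycemia related adverse events should be collected up to 9 weeks after first dose of study treatment".

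**Tabulation.** SAP 2.1.1.9 closes the on-treatment interval at "date of last administration of study treatment + 30 days". SAP 2.1.1.5 defines that date as "the last date when a non-zero dose of any component of the study treatment", so it covers alpelisib, fulvestrant, dapagliflozin and metformin XR. SAP 2.1.1.9 then states: "Safety summaries and selected summaries of deaths will summarize only on-treatment assessments/events". SAP 2.7.1 adds: "Summary tables for adverse events (AEs) will include only AEs that started or worsened during the on-treatment period, the treatment-emergent AEs". AEs outside the interval are listed by treatment group and flagged. Protocol 12.5.2 sets the same limit: "Safety summaries (tables, figures) include only data from the on-treatment period with the exception of baseline data". Neither document makes an exception for the extended hyperglycemia collection.

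**Primary endpoint.** SAP 2.5.1 counts any glucose value above 250 mg/dL from Cycle 1 Day 8 to Cycle 3 Day 8, with visit windows out to Cycle 3 Day 11. Under SAP 2.5.3, severe hyperglycemia "events collected after discontinuation of alpelisib or without any exposure to alpelisib will be used for the primary endpoint summary". SAP 2.5.2 reports the percentage per arm without confidence intervals.

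**What remains after termination.** SAP Section 4 limits safety summaries to AEs, deaths and SAEs. Other safety endpoints are only listed, for participants with notable values.

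**The concern.** Collection and tabulation run on different clocks. Collection is counted from the first dose and ends at a fixed study day. Tabulation is counted from the last dose and ends earlier the sooner a participant stops everything. Between the two end dates, sites report hyperglycemia AEs because the protocol asks for them, and the tables then leave those AEs out.

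Hyperglycemia is the subject of this trial, and after termination only two kinds of by-arm output still describe it: the percentage with glucose above 250 mg/dL, and the AE tables. The percentage is blind to anything milder. A late Grade 1-2 hyperglycemia AE, which may have been reported because it needed therapy (a criterion in protocol 10.1.1), is therefore in neither. A late severe episode can count in the primary endpoint summary while its AE is missing from the Grade 3-and-above table, and the SAP does not tell the reader why.

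**Working it through.** **Inputs**
- Cycle length 28 days (protocol Section 3).
- AE collection to 9 weeks after first dose (protocol 10.1.1).
- On-treatment to last dose of any component + 30 days, inclusive (SAP 2.1.1.5 and 2.1.1.9).
- Visit tolerance ±3 days (protocol Table 8-1; protocol 6.1.5 for this collection).

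**Step 1: reproduce the protocol's 9 weeks.** Cycle 3 Day 8 is study day 2 × 28 + 8 = 64. That is 63 days after Day 1, and 63 / 7 = 9.0 weeks. Then 9 − 1 = 8 and 9 − 2 = 7 match the two worked examples. The collection horizon is therefore the end of the primary endpoint window.

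**Step 2: days collected but not tabulated.** Let L be the study day of the last dose of any component. On-treatment ends on day L + 30, so

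days excluded = max(0, 64 − (L + 30)).

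Days after stopping, up to Day 64, are 64 − L. With the 3-day tolerance, 67 replaces 64.

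| L | On-treatment to | Excluded, to Day 64 | Excluded, to Day 67 |
|---|---|---|---|
| 7 | 37 | 27 of 57 (47%) | 30 of 60 (50%) |
| 14 | 44 | 20 of 50 (40%) | 23 of 53 (43%) |
| 21 | 51 | 13 of 43 (30%) | 16 of 46 (35%) |
| 28 | 58 | 6 of 36 (17%) | 9 of 39 (23%) |
| 33 | 63 | 1 of 31 (3%) | 4 of 34 (12%) |
| 34 | 64 | 0 | 3 of 33 (9%) |
| 37 | 67 | 0 | 0 |

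Alpelisib starts on Cycle 1 Day 8, so the L = 7 row is a participant with no alpelisib exposure and should not be read as typical. A fulvestrant injection given on schedule on Cycle 2 Day 1 (Day 29) makes L at least 29. The exclusion is then at most 64 − 59 = 5 days, or 67 − 59 = 8 with the tolerance.

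**Step 3: where a late event still appears.** Take an AE that starts after day L + 30 and by Day 64.

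| Late event | AE/SAE tables | Primary endpoint summary | Flagged by-arm listing |
|---|---|---|---|
| Glucose value above 250 mg/dL in the window | No | Yes | Yes |
| Grade 1-2, or no value above 250 mg/dL | No | No | Yes |

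Only the second row is lost from every by-arm summary.

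**The case against.** The case against acting is substantial.

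- **The extended collection already serves its main purpose.** It runs to the end of the primary endpoint window, and SAP 2.5.3 uses post-discontinuation values there. A reader might infer that late severe hyperglycemia vanishes from the comparison between arms. It does not: a qualifying glucose value counts under treatment policy, and SAP 2.7.4 combines central and local laboratory data. This stands.
- **Few participants can be affected.** A reader might infer that all early stoppers lose events. Anyone who takes any component on Day 34 or later (Day 37 with the tolerance) loses nothing. Protocol 6.1.5 lets the antihyperglycemic agents continue after alpelisib stops and ties their discontinuation to fasting glucose returning to normal or baseline, so a participant who is still hyperglycemic will often remain inside the window. The same section expects hyperglycemia typically to resolve once alpelisib stops. This stands.
- **The SAP follows the protocol.** Protocol 12.5.2 has the same restriction, so this is not an SAP departure. The gap lies between collection and summary, in both documents. This stands.
- **An extension would not equalise follow-up.** The AE tables cover up to 12 cycles plus 30 days, so observation time differs between participants anyway. The equal-window measure is the primary endpoint summary. This stands, and equal observation is not a reason for the change.
- **Laboratory grades and reported AEs differ by design.** Protocol 10.1.1 makes an abnormal value an AE only if it meets stated criteria. That explains some mismatch, but not one created by a calendar cut-off.
- **A hyperglycemia-only window inside the standard tables would mix windows** within system organ class and Grade 3-and-above totals, and the SAP does not define hyperglycemia-related. This stands and shapes the fix.

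None of this gives late milder events a place in any by-arm summary.

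**Conclusion.** The gap is real and small. Following both documents as written, hyperglycemia-related AEs that the protocol asks sites to collect are left out of the by-arm AE tables when they start more than 30 days after the last dose of every component and by Day 64 (Day 67 with the tolerance). Only participants off all components by Day 33 (Day 36) can be affected. Once alpelisib has been started on schedule (L of at least 8), the most that can be excluded is 64 − 38 = 26 days, or 29 with the tolerance.

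The loss is complete, apart from the listings, for Grade 1-2 events and for events without a value above 250 mg/dL. For late severe events with a qualifying value it is confined to the AE or SAE table entry.

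The day counts assume that study day is counted from first dose and that L covers all components, as the SAP defines. The documents do not say how many participants stopped this early or how many such AEs occurred, so neither an event count nor a difference between arms can be derived. Claims of bias between arms go beyond what they support.

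**What to change.** Leave the standard on-treatment AE tables as they are. Add to SAP 2.7.1 one separate by-arm summary of hyperglycemia-related AEs, by maximum grade, covering AEs that start or worsen from first dose to the later of last dose of any component + 30 days and study Day 64 (+3 days). State the preferred-term list that defines hyperglycemia-related. If hyperglycemia is one of the AESI groupings that protocol 12.5.2 assigns to the case-retrieval sheet or the SAP, that grouping is the natural source. Footnote the window, and record the addition in SAP Section 4 as a change from protocol 12.5.2.

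**Cost.** One extra table, one derivation flag and a term list, all on data the protocol already collects. The small downside is a table whose window differs from the other AE tables, which the footnote discloses.
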